3.4.2. Adverse Events

All safety endpoints will be summarized using descriptive statistics and will be by dose cohort for phase 1 subjects and by MDS/CMMML disease cohort for phase 2a subjects treated at RP2D and schedule using the FAS population.

All AEs will be coded based on the Medical Dictionary for Regulatory Affairs (MedDRA; Version 17.0 or higher). An AE will be considered a treatment emergent adverse event (TEAE) if the onset is after the first dose of study drug or if the condition was present at baseline but worsened after the first dose. All other AEs will be considered preexisting events.

All AEs for each subject will be listed, including Treatment Emergent status, intensity grading, relationship to study drug, action taken and outcome. Subject listings of deaths, serious TEAEs, and TEAEs leading to treatment discontinuation will be provided. Summary tables will be prepared to examine TEAE severity and relationship to study treatment.

TEAE summaries will be produced separately for each dose cohort for subjects in Phase 1 and by MDS/CMMML disease cohort for subjects in Phase 2a. All TEAE summaries will show the number and percentage of subjects experiencing at least 1 TEAE for each preferred term, arranged by system organ class, and the number of unique occurrences of the event. Separate summaries will be produced by relationship to study medication, and by severity, and for those events with an incidence of at least 2% in any group or overall. Subjects with multiple events will be counted only once per SOC and preferred term. For each level of summarization, the event with the highest level of severity, grade, or strongest drug relationship will be presented. TEAEs with Grade 3 or Grade 4 and drug-related TEAEs with Grade 3 or Grade 4 will be summarized. TEAEs leading to study drug interruption or discontinuation, Grade 3 and 4 TEAEs, Serious TEAEs will be provided in a separate listing.

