1.7.2. U.S. Phase 1/2a Study

Study FF1050101US101 is ongoing in the United States in patients with AML, MDS or CMML. In Phase 1, dose levels of 50, 100, 200, 300, 400 and 500 mg/m² BID for 14 days, followed by 14 days off therapy, or 400 mg/m² BID for 21 days, followed by 7 days off therapy, repeated every 28 days have been studied to date. A total of 33 patients have been treated to date on study (25 AML, 8 MDS).

Three events of drug-related atrial fibrillation (Grade 2) were reported in 2 subjects at a dose of 500 mg/m² BID (Cohort 6). Study drug was suspended in both subjects and all events resolved with oral metoprolol treatment. These events were medically important events and thus met the definition of dose-limiting toxicity (DLT). No further enrollment was made at this dose level. The maximally tolerated dose (MTD) was declared at 1 dose level below the dose eliciting DLT, 400 mg/m² BID, and this cohort was expanded to 6 subjects. No DLTs have been observed in N=7 total subjects treated at 400 mg/m² BID x 14 days.

At the MTD of 400 mg/m² BID, Cohort 7 was added to extend the BID dosing schedule to 21 days followed by 7 days off, repeated every 28 days (=1 cycle) (Amendment 3). No DLTs occurred have occurred to date.

At the MTD of 400 mg/m² BID, Cohort 8 was added to extend the BID dosing schedule to 28 days continuous dosing (=1 cycle) (Amendment 4). No DLTs have occurred to date.

The median number of prior treatments is 2 (range 1 - 7), all relapsed or refractory to prior hypomethylating agents (azacitidine, decitabine). The median number of treatment cycles is 2 (range 1 – 28).

The most common AEs include Grade 1 or 2 fatigue, diarrhea, and nausea, with drug-related Grade 3 or 4 AEs reported for 1 patient in the 200 mg/m² BID dose group (thrombocytopenia, neutropenia and bone marrow aplasia) and 1 patient in the 300 mg/m² BID dose group (mucositis); the events resolved without sequelae.

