Partial remissions have occurred in 3 AML patients (50, 100 and 400 mg/m² BID) after 1 – 3 cycles, lasting for at least 28, 5 and 6 cycles, respectively. A total of 8/25 (32%) AML patients, including the 3 PRs, have attained stable disease control with no disease progression over 4 – 28 cycles. A marrow complete response was achieved in 1 MDS patient treated at 400 mg/m² BID x 14 days after 1 cycle and was sustained for 14 cycles. A major platelet response was observed in 1 patient treated at 400 mg/m² BID x 21 days, sustained for 1 cycle. Four of 8 MDS patients (50%), including the marrow CR, attained stable disease control with no disease progression over 3, 5, 14 and 17 cycles, respectively.

FF-10501-01 was rapidly absorbed with mean T_{max} of 2.74 hours and mean $t_{1/2}$ of 4.05 hours. Drug exposure (AUC_{0-24} and AUC_{course}) increased with dose in a near linear manner.

Potent suppression of circulating xanthosine monophosphate (XMP), a marker of IMPDH activity, has been observed following FF-10501-01 administration on Day 1 of Cycles 1 and 2 at doses $\geq 50 \text{ mg/m}^2 \text{ BID}$.

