5.5. Supportive Care Guidelines

- Medications may be administered for the management of symptoms associated with the administration of FF-10501-01, as required.
- Prophylactic pre-medication will not be used routinely. Adequate treatment for nausea and/or vomiting and diarrhea is permitted during Cycle 1. After Cycle 1, prophylaxis of nausea and/or vomiting and diarrhea is permitted.
- Granulocyte stimulating growth factors (e.g., G-CSF or GM-CSF) are not allowed during Cycle 1 except for the following situations (defined as DLTs): Grade 4 neutropenia lasting 7 days or more, or failure of the absolute neutrophil count (ANC) to recover to Grade 1 within 12 weeks. After Cycle 1, use of granulocyte growth factors are allowed for prophylaxis or management of neutropenia.
- Erythropoiesis-stimulating agents, transfusions, etc. are permitted for management of hematologic toxicities.

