7.1.4. Adverse Event Reporting Period

The adverse event reporting period begins from the date of the first dose of study drug to 28 days following the last dose of study drug.

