1.3. Treatment(s)

1.3.1. Treatment Assignments

Phase 1:

14-day Schedule: Following Screening, a total of 6 cohorts of 3 subjects each received oral doses of 50, 100, 200, 300, 400 or 500 mg/m² BID per day (100, 200, 400, 600, 800 or 1000 mg/m²/day) for 14 days, followed by 14 days off, repeated every 28 days (= 1 cycle). Three events of drug-related atrial fibrillation (Grade 2) were reported in 2 subjects at a dose of 500 mg/m² BID (Cohort 6). Study drug was suspended in both subjects and all events resolved with oral metoprolol treatment. These events were medically important events and thus met the definition of dose-limiting toxicity (DLT). No further enrollment was made at this dose level. The maximally tolerated dose (MTD) was declared at 1 dose level below the dose eliciting DLT, 400 mg/m² BID, and this cohort was expanded to 6 subjects. No DLTs were observed in N=7 total subjects treated at 400 mg/m² BID x 14 days.

21-day Schedule: At the MTD of 400 mg/m² BID, Cohort 7 was added to extend the BID dosing schedule to 21 days followed by 7 days off, repeated every 28 days (=1 cycle).

28-day Schedule: At the MTD of 400 mg/m² BID, Cohort 8 is added to extend the BID dosing schedule to 28 days continuous dosing each 28 days (=1 cycle).

DLT is defined as Grade 4 hematologic toxicity lasting 7 days or more; Grade 3 nonhematologic toxicity of any duration not amenable to supportive care; failure of platelets, absolute neutrophil count (ANC), or hemoglobin (Hb) to recover to Grade 1 within 12 weeks despite use of platelet and red blood cell (RBC) transfusions and/or growth factors; febrile neutropenia (defined as ANC<1000/mm³ with a single temperature of > 38.3°C or sustained temperature of ≥ 38°C for over one hour); Grade 3 thrombocytopenia associated with bleeding; or other important medical event.

At the MTD of 400 mg/m² BID, the 28-day continuous schedule of administration resulted in a higher rate of adverse events with no additional efficacy versus the 21-day schedule. Therefore, the recommended Phase 2 dose (RP2D) and schedule was determined to be 400 mg/m² BID on a 21-day schedule of administration, repeated every 28 days.

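### Phase 1 TEAE percentages by dose cohort depend on time on treatment; adding Cycle 1 tables would give a common-window comparison at little cost

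*SAP*

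**What the plan says.** **Measure.** SAP 3.4.2: "All TEAE summaries will show the number and percentage of subjects experiencing at least 1 TEAE for each preferred term", together with a count of occurrences. In Phase 1 the grouping is by dose cohort: "TEAE summaries will be produced separately for each dose cohort for subjects in Phase 1". The table list in SAP 4.1.6.2 has no table limited to Cycle 1 and none with a time denominator. Protocol 8.3.1.1 adds neither.

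**Window.** An event is treatment-emergent "if the onset is after the first dose of study drug", or if a baseline condition worsens after that dose. The SAP definition gives no end. Protocol 7.1.4 says that the reporting period "begins from the date of the first dose of study drug to 28 days following the last dose of study drug".

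**Time on drug.** Treatment continues to progression or unacceptable toxicity (Protocol 5.3). Protocol 1.7.2 gives a median of 2 cycles and a range of 1 to 28 among 33 treated subjects. The partial remissions at 50, 100 and 400 mg/m² BID are described as "lasting for at least 28, 5 and 6 cycles, respectively".

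**Cohort label.** Under SAP 1.4.1 the cohort number does not change when a subject's dose goes up or down. SAP 1.3.2 lets subjects already on study move to a longer schedule.

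**Size.** SAP 2.1 plans 3 to 6 subjects per cohort; 7 were treated at 400 mg/m² BID for 14 days (SAP 1.3.1).

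**The concern.** Safety and tolerability is the primary objective, and the cohort-by-cohort TEAE tables are its main display. The percentage of subjects who have ever had an event cannot fall as treatment goes on. Two cohorts with the same risk per cycle will therefore show different percentages if one is treated longer. With 3 to 7 subjects per cohort, one long-treated subject is between 1/7 = 14% and 1/3 = 33% of the denominator.

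The fixed cohort label adds to this. A late event can be counted under a dose or schedule that the subject has already left. SAP 1.4.1 speaks only of dose changes, so the handling of a schedule change is my reading, but no rule moves such a subject to another cohort.

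At stake is what a reader may conclude when comparing columns. Such comparisons are made: SAP 1.3.1 reports that "the 28-day continuous schedule of administration resulted in a higher rate of adverse events with no additional efficacy versus the 21-day schedule".

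**Working it through.** **1. Stated figures.** No number in the plan is disputed. The sizes in SAP 2.1 reproduce: 8 cohorts × 6 = 48, and 48 + 20 = 68.

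**2. Inputs from the documents.** Window open from first dose to 28 days after last dose (Protocol 7.1.4). Time on drug 1 to 28 cycles, median 2 (Protocol 1.7.2). Minimum cohort size 3 (SAP 2.1).

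**3. Inputs assumed.** A constant risk h per cycle of a given TEAE, at 2%, 5%, 10% and 20%. A cohort of three treated 28, 2 and 2 cycles, set against a cohort of three with risk 2h treated 2 cycles each. The documents give neither the risks nor the cycle counts of whole cohorts.

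**4. Formula.** Expected crude incidence after c cycles is 1 − (1 − h)^c. A cohort's expected percentage is the mean of this over its subjects.

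At h = 10%:
- 28 cycles: 1 − 0.9^28 = 94.8%
- 2 cycles: 1 − 0.9^2 = 19.0%
- first cohort: (94.8 + 19.0 + 19.0)/3 = 44.3%
- second cohort, risk 20%: 1 − 0.8^2 = 36.0%

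| h per cycle | 1 cycle | 2 cycles | 28 cycles | Cohort 28, 2, 2 at h | Cohort 2, 2, 2 at 2h | Order reversed? |
|---|---|---|---|---|---|---|
| 2% | 2.0% | 4.0% | 43.2% | 17.0% | 7.8% | yes |
| 5% | 5.0% | 9.8% | 76.2% | 31.9% | 19.0% | yes |
| 10% | 10.0% | 19.0% | 94.8% | 44.3% | 36.0% | yes |
| 20% | 20.0% | 36.0% | 99.8% | 57.3% | 64.0% | no |

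A Cycle 1 table would be expected to show h against 2h in every row, for example 10% against 20%.

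**5. Opposite extreme.** If a given TEAE arises only in Cycle 1, the all-cycles and Cycle 1 percentages are equal and the distortion is zero.

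**6. Can the planned exposure table supply the denominator?** SAP 3.4.1 counts days from first to last dose within each cycle and, where dosing was interrupted, scales them by dose taken over dose prescribed. Without interruption, one 28-day cycle counts as 14, 21 or 28 days depending on the schedule. The same number of events per cycle would then give a rate per drug-day 28/14 = 2 times as high on the 14-day schedule as on continuous dosing. Among the 14-day cohorts the figure follows cycles more closely, but interruptions and later schedule extensions still alter it. It measures dosing, not time at risk.

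**The case against.** **The formal dose-toxicity rule already has a common window.** Escalation depends on DLTs by Day 28 (Protocol 3.1, SAP 1.3.2), the MTD was declared on DLTs, and DLTs have their own listing (SAP 4.3). No tests are planned (SAP 2.4.2). This stands, and it confines the point to the descriptive TEAE tables.

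**Exposure and occurrences are both tabulated by cohort.** A reader can see an imbalance in exposure and, from n and the mean, approximate occurrences per drug-day. This stands in part. Step 6 shows why the figure fails across schedules, and first-event rates would need recalculation from the listings.

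**The illustration is constructed.** The 28, 2, 2 pattern is assumed; the range of 1 to 28 is over all 33 subjects. The 44% against 36% is about 0.25 of a subject in a cohort of three (0.083 × 3). Protocol 1.3.3 puts white cell and platelet nadirs at 2 to 3 weeks with the predecessor product, so some toxicity is early. This stands: the table shows what can happen, not what did.

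**Adverse event visits become fewer.** Protocol 6.2 and 6.3 schedule five assessments in Cycle 1 and one or two per cycle afterwards. A reader might infer a gap in collection, but Appendix D marks assessment as continuous, so this is a secondary matter of detection. Fewer visits, and the rule that "After Cycle 1, prophylaxis of nausea and/or vomiting and diarrhea is permitted", would lower later observed incidence. Both work against accumulation.

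**Conclusion.** The point holds as a cheap improvement to reporting. TEAE percentages by Phase 1 cohort depend on time on treatment, and no planned table puts the cohorts on a common window. That dependence follows from the definition of the measure and needs no assumption about risk. Its size does: the reversals at 2%, 5% and 10% per cycle, and the absence of one at 20%, rest on constant risk and invented cycle patterns.

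Three stronger readings are not supported:
- **That the MTD or the escalation decisions are compromised.** They use a fixed Day 28 window.
- **That low doses are made to look more toxic.** The response of at least 28 cycles was at 50 mg/m² BID, but Protocol 1.7.2 also reports, at 400 mg/m² BID, a marrow response sustained for 14 cycles and a partial remission of at least 6. The direction is unknown.
- **That the preference for the 21-day over the 28-day schedule is an artefact.** SAP 1.3.1 does not say how its adverse event rate was calculated, and time on drug in Cohorts 7 and 8 is not given.

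One limit: the SAP text between 2.4.4 and 2.4.6 was not available to me, so I cannot exclude that it bears on this.

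**What to change.** In SAP 3.4.2 and 4.1.6.2:

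1. Add Cycle 1 versions of the TEAE, Grade 3 or higher TEAE and drug-related TEAE tables, by dose and schedule cohort, and name them as the basis for comparing cohorts. Counting onsets on Days 1 to 28 would match the DLT window. Because reporting runs to 28 days after the last dose, that window is covered even for subjects who stop early, apart from death or loss of contact.
2. Keep the all-cycles tables for late toxicity, and show in each column the number of treatment cycles (28-day cycles started).

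Rates per patient-cycle are optional. They assume constant risk, and one long-treated subject can dominate: in the illustration, up to 28 of 28 + 2 + 2 = 32 patient-cycles.

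Cost: a few extra tables from event and dosing dates already collected, with no new data or visits. Downside: Cycle 1 tables omit late toxicity, so they must sit beside the all-cycles tables and not replace them.

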
Safety: Safety will be assessed through the monitoring of adverse events (AEs), clinical laboratory parameters (hematology, serum chemistry, urinalysis), vital sign measurements, ECGs and physical examinations. Adverse events will be classified according to the Medical Dictionary for Regulatory Affairs (MedDRA) and graded according to the National Cancer Institute Common Terminology Criteria for Adverse Events (NCI CTCAE) version 4.03.
 
Efficacy: Efficacy assessment for AML will be performed using a modification of the recommendations of the International Working Group for Diagnosis, Standardization of Response Criteria, Treatment Outcomes, and Reporting Standards for Therapeutic Trials in Acute Myeloid Leukemia. Efficacy assessments for subjects with MDS or CMML will be performed using a modification of the International Working Group Response Criteria in Myelodysplasia. Efficacy assessments for any subject may be performed at other time points at the discretion of the investigator.
 
Pharmacokinetics: Pharmacokinetic determinations will be performed.
 
Pharmacodynamics: XMP will be determined in peripheral blood.
	

Sponsor: FUJIFILM Pharmaceuticals U.S.A., Inc.	Protocol Number: FF1050101US101
Investigational Product:	
FF-10501-01 is an oral antimetabolite anticancer drug. It is a competitive inhibitor of inosine 5'-monophosphate dehydrogenase (IMPDH). FF-10501-01 is supplied in 50 and 200 mg tablets for oral administration. FF-10501-01 should be stored at room temperature (20 – 25 °C).	
FF-10501-01 is manufactured for FPHU by Patheon (Missisauga, Ontario, Canada) and will be provided by the sponsor (FPHU).	
Reference Therapy: None	
Statistical Methods:	
Safety Endpoint Analyses:	
Safety endpoints for AEs include the following: incidences of all treatment-emergent adverse events (TEAEs) and all serious adverse events (SAEs); incidences of TEAEs and SAEs by severity; incidences of TEAEs and SAEs by relationship to study medications; incidences of all Grade 3 and 4 TEAEs and by severity and relationship to study medications; and discontinuation of subjects from the study due to AEs or death. Safety endpoints for AEs, clinical laboratory tests, vital signs, ECGs and physical examinations will be specified in the statistical analysis plan. All safety endpoints will be summarized using descriptive statistics.	
Efficacy Endpoint Analyses:	

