4.1.6.2. Adverse Events Summaries

- Summary of Treatment Emergent Adverse Events

- Treatment Emergent Adverse Events by System Organ Class and Preferred Term
- Treatment Emergent Adverse Events by Relationship to Study Drug
- Summary of Treatment Emergent Adverse Events by Severity
- Grade 3 and Grade 4 Treatment Emergent Adverse Events
- Drug-related Grade 3 and Grade 4 Treatment Emergent Adverse Events
- Treatment Emergent Adverse Events by System Organ Class and Preferred Term with at least 2% Incidence in any Group or overall

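### The high-grade TEAE tables stop at Grade 4, so fatal events fall outside them, and no table named in the SAP crosses Grade 5 with drug relationship

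*SAP*

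**What the plan says.** **High-grade tables.** SAP 3.4.2 states that "TEAEs with Grade 3 or Grade 4 and drug-related TEAEs with Grade 3 or Grade 4 will be summarized". Section 4.1.6.2 has two matching titles, one for all causes and one reading "Drug-related Grade 3 and Grade 4 Treatment Emergent Adverse Events". The limit is not an SAP invention: the safety endpoints in the protocol synopsis include "incidences of all Grade 3 and 4 TEAEs and by severity and relationship to study medications".

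**Scale and recording.** Protocol 7.1.5.1 grades events from 1 to 5, with 5 meaning death. Under protocol 7.1.7 the cause of a death becomes the SAE term, and every SAE is also entered on the AE form. Fatal events are therefore in the AE data with a grade.

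**Counting rule.** A subject counts once per system organ class and preferred term, and at each level "the event with the highest level of severity, grade, or strongest drug relationship will be presented".

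**Other AE tables.** SAP 3.4.2 adds that "Separate summaries will be produced by relationship to study medication, and by severity". Section 4.1.6.2 names "Summary of Treatment Emergent Adverse Events by Severity" and "Treatment Emergent Adverse Events by Relationship to Study Drug" alongside the table by organ class and preferred term. None of these has a grade cap.

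**Deaths and serious events.** The SAP plans listings: "Subject listings of deaths, serious TEAEs, and TEAEs leading to treatment discontinuation will be provided". Section 3.4.6 likewise lists deaths. Protocol 8.3.1.1 goes further. It promises SAE summaries overall, by relationship and by severity, and counts with percentages of subjects who leave the study because of AEs or death.

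**The concern.** Safety and tolerability is the primary objective (protocol 2.1, SAP 1.2.1), and SAP 1.3.1 says that the Phase 2 schedule was chosen partly because continuous dosing produced more adverse events. Readers usually turn to the high-grade table, and above all the drug-related one, to compare severe toxicity between cohorts. A table that ends at Grade 4 leaves out the worst outcome.

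Protocol 7.1.1 keeps worsening of the underlying disease out of the AE data when it is captured as efficacy. The Grade 5 TEAEs that remain should therefore lean towards deaths not put down to progression, where the question of drug relationship matters most.

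**Working it through.** The plan gives no figure to reproduce. The check is to trace where a fatal TEAE is counted under the stated rules.

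**Step 1: the filter.** A TEAE whose only record is Grade 5 meets neither Grade 3 nor Grade 4 and is outside both high-grade tables under any reading. Protocol 7.1.5 asks for the maximum intensity of each AE, so an event that worsens to death may be held as a single Grade 5 record. The documents do not say whether worsening opens a new record.

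**Step 2: order of operations.** Suppose a subject has separate Grade 3 and Grade 5 records of one term. If worst grade is selected first, the subject is Grade 5 and drops out. If the filter comes first, the subject stays, but appears as non-fatal. The SAP does not say which applies.

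**Step 3: an assumed example.** Take 20 subjects (the planned Phase 2a number) and one preferred term. All counts are illustrative.

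| Subject | Recorded grades | Drug-related |
|---|---|---|
| 1 | 3, then 5 | yes |
| 2 | 5 | yes |
| 3 | 4 | no |
| 4 | 3 | yes |
| 5 | 2 | no |

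| Table | Worst grade first | Filter first |
|---|---|---|
| Grade 3–4, all causes | subjects 3, 4: 2/20 = 10% | subjects 1, 3, 4: 3/20 = 15% |
| Grade 3–4, drug-related | subject 4: 1/20 = 5% | subjects 1, 4: 2/20 = 10% |
| Grade 3 or higher, all causes | subjects 1–4: 4/20 = 20% | same |
| Grade 3 or higher, drug-related | subjects 1, 2, 4: 3/20 = 15% | same |

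The uncapped tables still count both fatal events. All TEAEs show 5/20, the by-severity table shows 2/20 at Grade 5, and the by-relationship table shows 3/20 related. The figure that no named table yields is drug-related and fatal, here 2/20 = 10%: the severity table is not split by relationship, and the relationship table is not split by grade.

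**Step 4: general size.** If k of N subjects in a row are lost, the Grade 3-or-higher rate is understated by k/N.

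- N = 20: k = 0, 1, 2, 3 gives 0, 5, 10 and 15 points. For instance, with 4 subjects at worst Grade 3–4 and 2 at Grade 5, the table shows 4/20 = 20% against 6/20 = 30%.
- N = 6: k = 1 gives 1/6 = 17 points.
- N = 3: k = 1 gives 1/3 = 33 points. A move from 33% to 0% when one event becomes fatal requires that this subject is the only contributor to the row, and either that worst grade is taken first or that the only record is Grade 5.

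**The case against.** **Deaths are visible elsewhere.** A reader might infer that drug-related deaths appear in no incidence table at all. The documents do not support that. A fatal drug-related TEAE enters the tables by organ class and preferred term, by relationship and by severity, and the last can show it as Grade 5. All AEs are also listed with grade, relationship and outcome, and deaths have their own listing. In cohorts of 3 to 6 and a group of 20, a reader can count drug-related deaths from those listings. This stands, and it confines the point to the high-grade tables and the missing cross of grade with relationship.

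**The SAP gives titles, not shells.** The general TEAE summary in 4.1.6.2 could turn out to contain a row for drug-related fatal events. That is possible, but nothing in the text specifies it.

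**The SAP follows the protocol.** It does: the Grade 3–4 limit is in the synopsis, so the limit is not a departure. That shows where the gap began without giving a reason for it. The absence of an SAE incidence table from 4.1.6.2 is a different matter, because protocol 8.3.1.1 promises one.

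**Little hangs on this table.** There are no formal hypothesis tests (SAP 2.4.2), and escalation rests on DLTs, which have a separate listing. This limits the consequence to reporting. Reporting of safety is nevertheless the study's primary purpose.

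**Conclusion.** The point holds in a limited form. Both high-grade TEAE tables exclude any TEAE recorded only as Grade 5. On one of two readings they also exclude a subject whose separately recorded Grade 3 or 4 event of the same term becomes fatal. The Grade 3-or-higher rate is understated by k/N. Since k is unknown, the percentages above are illustrations and not predictions.

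It would go too far to say that fatal events vanish from the report, or that a cohort with more deaths must look safer overall. Only the high-grade tables have this defect, and the by-severity table works against such a misreading. What is missing is a table that identifies fatal events as drug-related. As the SAP's outputs are named, that information sits only in listings.

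The conclusion assumes that the tables are programmed as their titles read and that fatal events carry Grade 5, as the protocol's scale provides.

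**What to change.** - In SAP 3.4.2 and the two high-grade titles in 4.1.6.2, replace the Grade 3/4 wording with Grade 3 or higher, with Grades 3, 4 and 5 shown separately and combined, for all TEAEs and for drug-related TEAEs. The drug-related version then supplies the missing Grade 5 count.
- Make the same change in the protocol synopsis, so that the two documents agree.
- State that each subject is classified by worst grade before the filter is applied and, in the drug-related table, by worst grade among drug-related events. With a Grade 3-or-higher filter the order no longer changes the combined count, but it still decides the grade under which a subject is shown.
- Add to 4.1.6.2 the SAE incidence tables, overall, by relationship and by severity, that protocol 8.3.1.1 promises.

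The cost is minor programming: a changed filter, changed titles and the SAE tables, with no new data to collect. The synopsis edit needs a protocol amendment, which under protocol 9.4 goes to the IRB. The reported severe-toxicity rate may come out slightly higher.
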